7.3.6.6 Baseline Period

The 6 months (183 days; defined as an inclusion criteria) prior to and including the cohort entry date will be set as the baseline period. Recognizing that a narrower (for time-varying covariates, etc.) or a broader (for chronic conditions) window of assessment may better capture patient characteristics of interest, specific covariates may be assessed using alternative time period(s). For example, while patients are required to have 6 months of continuous medical and pharmacy coverage prior to cohort entry to be eligible for inclusion in the study, presence of AD and PN will be assessed up to 12 months prior to pregnancy, as data allow.

7.3.6.7 Follow-up

For each weekly cohort, pregnancies will be followed from the date after cohort entry until the earliest of the end of pregnancy, disenrollment from the health plan (for claims databases), 8 weeks with no clinical activity recorded (for the linked claims-EHR database or EHR-only databases) or the end of the study period (31 March 2032 or latest data available). Each linked infant will be followed from delivery until the earliest of end of first year of life, disenrollment from the health plan (for claims databases), 8 weeks with no clinical activity recorded (for the linked claims-EHR database or EHR-only databases) or the end of the study period. Follow-up for spontaneous abortion and elective termination will be censored at 20 weeks' gestation, and follow-up for preterm birth will be censored at 37 weeks' gestation. The censoring events for each outcome are summarized in [Table 2](#).

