7.3 Setting

7.3.1 Source Population

The source population for this study will include pregnancies that begin (based on ECD) between 12 August 2024 and 31 March 2032 (or most recent data available at the time of the last data extract).

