7.3.2 Inclusion Criteria

Pregnancies among women who meet the following criteria will be eligible for inclusion in the study:

- An ECD between 12 August 2024 and 31 March 2032
- For claims data sources, continuous health plan enrollment with complete medical and pharmacy benefit coverage from 6 months before and including cohort entry (only applicable to the pregnant woman)
- For linked claims-EHR data sources:
 - Pharmacy (but not medical) coverage during the full pregnancy period (as described in [Table 1](#)) will be required to ensure dispensings of cohort defining drugs are captured. (A shorter period of continuous enrollment will be required for linked claims-EHR data sources compared with the claims databases because pharmacy claims will be used primarily for exposure assessment, while covariates will be assessed from the EHR data).
 - Presence of at least one outpatient clinical visit at least 6 months prior cohort entry (to establish a 6-month baseline period for assessment of AD and PN as well as clinical covariates).
- Evidence of moderate to severe AD or PN ascertained using appropriate algorithms

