Cohort entry will be set at the date of dispensing in the Nemolizumab Cohort (i.e., the earliest nemolizumab administration date during a pregnancy) and the Other AD/PN Treatment Cohort,

and the corresponding day of gestation among unexposed pregnancies, rounded down to the nearest week. For example, for pregnancies entering the Week 8 Cohort, we will first select all pregnancies with no nemolizumab or other AD/PN treatment from 5 times the half-life before ECD through 7 weeks' + 6 days' gestation. Then, we will assign the pregnancies that receive nemolizumab during Week 8 (8 weeks + 0 days through 8 weeks + 6 days) to the nemolizumab-exposed group, those that received another AD/PN treatment to the other treatment-exposed group, and those that did not receive nemolizumab or another AD/PN treatment during Week 8 to the unexposed group. Cohort entry among the Week 8 nemolizumab and comparator cohorts will be set to 8 weeks' + 0 days. The pregnancies in the Week 8 exposed cohort will no longer be eligible for inclusion in subsequent weekly cohorts. However, the pregnancies in the Week 8 unexposed group will go on to be eligible for inclusion in the Week 9 Cohort, at which point their exposure status would be reassessed during Week 9 (9 weeks + 0 days through 9 weeks + 6 days). A pictorial depiction of this process can be found in Figure 1 and key pregnancy dates can be found in Table 1. If the study size does not permit weekly sequential cohorts, the cohorts may be collapsed into longer (e.g., 2-week, 4-week) intervals as needed.

Figure 1 Sequential cohort design, depicting an example of cohort entry for the Week 7 and Week 8 cohorts

Abbreviations: AD, atopic dermatitis; ECD, estimated conception date; PN, prurigo nodularis

Table 1 Pregnancy dates

Date	Definition
LMP	First day of last menstrual period 0 gestational weeks ^{0/7 days}
Gestational age	Weeks of gestation Anchored by LMP Number of completed weeks elapsed after LMP

Date	Definition
ECD	Estimated as LMP + 14 days 2 gestational weeks ^{0/7 days}
First trimester	Begins at ECD minus 5 times the half-life of the treatment Ends at LMP + 97 days
Second trimester	Begins at LMP + 98 days Ends at LMP + 195 days
Third trimester	Begins at LMP + 196 days Ends at pregnancy outcome
Pregnancy period	Begins at ECD minus 5 times the half-life of the treatment Ends at pregnancy outcome

Abbreviations: ECD, estimated conception date; LMP, first day of last menstrual period

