Stillbirth	Entire pregnancy	Week 2 – Week 40	Later of cohort entry or 20 weeks + 0 days	End of pregnancy, disenrollment from the health plan/8 weeks of no clinical activity, or the end of the study period
MCM	First trimester	Week 2 – Week 13	Delivery	First year of life, disenrollment from the health plan/8 weeks of no clinical activity, or the end of the study period
SGA birth	Entire pregnancy	Week 2 – Week 40	Delivery	First year of life, disenrollment from the health plan/8 weeks of no clinical activity, or the end of the study period

Abbreviations: ECD, estimated conception date; EHR, electronic health record; MCM, major congenital malformation; SGA, small for gestational age

¹ For individuals with a cohort entry date after the pre-specified start of follow-up, follow-up begins at cohort entry. For example, for cohorts beginning at 24 gestational weeks, follow-up for stillbirth will begin at 24 gestational weeks.

² For EHR and linked claims-EHR data sources, pregnancies will be censored at the end of 8 weeks of no clinical activity. Since pregnant women should regularly interact with the healthcare system, this censoring criterion will indicate loss to follow-up in the database.

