7.4.2.2 Infant Outcomes

7.4.2.2.1 MCM

MCMs will be defined based on guidelines from the New York State Department of Health Congenital Malformations Registry, National Birth Defects Prevention Network, and/or the European Surveillance of Congenital Malformations. Live births will be followed for up to one year to identify MCMs that may not be detected until after birth. All identified MCMs will be counted, overall, and classified by body system. Operational definitions may be modified to add or remove MCM-specific ICD-10-CM codes based on clinician input or newly identified algorithms in the literature. Minor congenital malformations will not be included in this definition. A list of ICD-10-CM diagnosis codes for MCMs can be found in [Appendix E](#).

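### The last eligible conception date and the end of follow-up are the same date, so late pregnancies are cut short and late infants miss their year of malformation follow-up.

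*Protocol*

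**What the plan says.** Protocol 7.3.2 (Inclusion Criteria) requires "An ECD between 12 August 2024 and 31 March 2032", with no qualifying clause. Sections 7.1 and 7.3.1 give the same window but let the upper limit depend on the data; 7.3.1 has "31 March 2032 (or most recent data available at the time of the last data extract").

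Section 7.3.6.7 (Follow-up) censors pregnancies at the earliest of several events, the last being "or the end of the study period (31 March 2032 or latest data available"). For infants it says "Each linked infant will be followed from delivery until the earliest of end of first year of life", again cut at disenrolment, inactivity or the end of the study period. Table 2 in 7.3.6.2 lists the MCM censoring events as "First year of life, disenrollment from the health plan/8 weeks of no clinical activity, or the end of the study period".

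Section 7.4.2.2.1 gives the reason for the infant year: "Live births will be followed for up to one year to identify MCMs that may not be detected until after birth". MCM is the primary outcome. Sections 7.7.3.2 and 7.7.3.3 analyse MCM and small for gestational age (SGA) as prevalences with robust Poisson regression, and the other outcomes with Cox models. Section 4 dates the start of extraction for the final report at 8 December 2032 and the complete analytic dataset at 24 October 2033.

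**The concern.** A pregnancy needs about nine months from conception to delivery, and the MCM definition relies on up to a further year of infant records. With one date serving as both the last eligible ECD and the end of follow-up, the latest pregnancies enter without time to supply these.

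Two distortions follow. Among the latest conceptions, only early outcomes and preterm births can be seen. Among somewhat earlier ones, infants are born but followed for less than a year, so malformations recognised after birth can be missed. The first two objectives are outcome frequencies, which are directly exposed to both. The protocol states no follow-up term for the Poisson analysis of MCM, so nothing in its text absorbs short infant follow-up. Section 7.1 expects uptake to take time, so exposed pregnancies may well be concentrated in the affected years.

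**Working it through.** **Inputs.** ECD window: 12 August 2024 to 31 March 2032, 2,789 days counting both ends (7.3.2). End of follow-up: 31 March 2032 or latest data (7.3.6.7). ECD: "Estimated as LMP + 14 days" (Table 1). Preterm: before 37 weeks (7.4.2.1.4). Extraction start and dataset completion: Section 4. Sample size: 1:4 ratio, 80% power, two-sided 0.05, MCM prevalence 3% (7.5, Table 3).

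**The plan's own figure.** For relative risk 2.5, p1 = 0.075, p2 = 0.03, r = 4 and the pooled p = (0.075 + 4 × 0.03)/5 = 0.039. The Fleiss formula without continuity correction is

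n = [1.96 × √(5 × 0.039 × 0.961) + 0.842 × √(4 × 0.075 × 0.925 + 0.03 × 0.97)]² / (4 × 0.045²) = 213.3, rounded up to 214 exposed live births.

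Then 214/(0.80 × 0.76) = 351.97, so 352 pregnancies, and 4 × 352 = 1,408. These match 7.5.

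**Days needed after ECD.** 37w0d is 259 − 14 = 245 days. 40w0d is 280 − 14 = 266 days. A 40-week birth plus a year is 266 + 365 = 631 days.

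**Share of the window affected.** With d the days of the window too late to meet a condition, the share is f = d/2,789 under uniform accrual and 1 − (1 − f)² under a linear rise from zero. Both shapes are assumptions; the protocol gives none. The second and third blocks hold the last ECD at 31 March 2032 and extend only follow-up.

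| Follow-up ends | Condition | Last ECD meeting it | d | Uniform | Linear rise |
|---|---|---|---|---|---|
| 31 Mar 2032 | 37w0d | 30 Jul 2031 | 245 | 8.8% | 16.8% |
| 31 Mar 2032 | 40w0d | 9 Jul 2031 | 266 | 9.5% | 18.2% |
| 31 Mar 2032 | 40w0d + 1 year | 9 Jul 2030 | 631 | 22.6% | 40.1% |
| 8 Dec 2032 | 37w0d | all | 0 | 0% | 0% |
| 8 Dec 2032 | 40w0d | 17 Mar 2032 | 14 | 0.5% | 1.0% |
| 8 Dec 2032 | 40w0d + 1 year | 18 Mar 2031 | 379 | 13.6% | 25.3% |
| 24 Oct 2033 | 40w0d + 1 year | 1 Feb 2032 | 59 | 2.1% | 4.2% |

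On 8 December 2032 the last admitted pregnancy is 252 days past ECD, or (252 + 14)/7 = 38 weeks. That is a best case, since 7.7.2 recognises that data sources lag.

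**Effect on MCM precision (illustration).** Suppose the 214 exposed live births were spread over the whole window and only infants with a full year were kept, with follow-up ending 31 March 2032. Then 214 × (1 − 0.226) = 166 remain under uniform accrual and 214 × (1 − 0.40) = 128 under the linear rise. Power at relative risk 2.5 falls from 80.1% to about 71% and 62%.

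**The case against.** The case for leaving the text alone has real substance.

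- *The dates need not coincide.* The inclusion criterion in 7.3.2 fixes the last ECD, while 7.3.6.7 lets follow-up run to the latest data. On that reading the preterm-only problem disappears. But 7.1 and 7.3.1 attach a similar clause to the ECD limit, so the text also allows both ends to move together. It cannot be said that they do. Even the favourable reading leaves 379 days without a full infant year.
- *Truncation was accepted.* The infant follow-up is worded as a maximum, and end of study is a listed censoring event. Section 7.10 compares observed with censored pregnancies, and 7.4.3.7 describes infant coverage. This stands, but none of it addresses the concentration of truncation in the last conceptions.
- *The comparison is largely protected.* Cox models handle administrative censoring, and matching on calendar week and gestational week makes truncation largely similar across cohorts. This stands.

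A reader might also infer more than the documents support:

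- That every conception in the last 266 days can show only losses, terminations or preterm births. The limit is 245 days; those conceived 245 to 266 days before the end can show early-term births.
- That the share unable to reach 40 weeks uses up the 20% of unobserved outcomes allowed in 7.5. Losses, terminations and preterm births in that group are observed, so the two quantities differ.
- That pregnancies in the last 631 days cannot supply the primary outcome. Most can deliver before the cut and contribute malformations coded at birth.
- That losses and preterm births will be over-reported. This depends on the denominator. Counting only completed pregnancies would raise those proportions; counting all entrants would lower a crude preterm proportion.

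**Conclusion.** The point holds in limited form and is worth correcting. Ending follow-up on the last eligible ECD leaves 8.8% of the window (16.8% under a linear rise) unable to reach 37 weeks, and 22.6% (40.1%) without a full infant year after a 40-week birth. Extending only follow-up to the start of extraction removes the first and reduces the second to 13.6% (25.3%).

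The consequence is distorted outcome frequencies, an MCM prevalence likely to miss malformations recognised after birth, and less MCM precision than the target implies. It is not a demonstrated bias in the relative risks or hazard ratios. The percentages rest on the assumed accrual shapes. The MCM concern further assumes that infants with short follow-up and no code count as unaffected, which the protocol does not state but its Poisson analysis would imply unless follow-up is built in.

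**What to change.** 1. Define the data end (last complete data at extraction) separately from the last eligible ECD, and use the same wording in 7.1, 7.3.1, 7.3.2, 7.3.6.7 and Table 2.
2. For outcome frequencies and SGA, set the last ECD at least 280 days (42 weeks' gestation) before the data end. Keep later pregnancies in the Cox models under administrative censoring.
3. For MCM, either set the data end late enough to give the last eligible birth a full year, or keep all linked live births and add an analysis limited to births at least 365 days before the data end.
4. When reporting accrual against 352, show how many pregnancies can be observed to delivery and how many through the infant year.

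**Cost.** Mostly wording and a date filter. With a data end of 8 December 2032, the 280-day rule puts the last ECD at 3 March 2032 and removes 28 days (28/2,789 = 1.0% of the window) from the frequency analyses. With a data end of 31 March 2032 it removes 280 days (10.0%).

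For MCM, keeping the 31 March 2032 ECD limit with a full infant year needs data to about 22 December 2033 (40-week birth). That is after the 24 October 2033 dataset milestone, so either the milestone or the last ECD would have to move. The added analysis avoids this. Simply dropping all late conceptions from the primary MCM analysis is not advised: it could remove 22.6% to 40.1% of accrual, including infants with malformations coded at birth.

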7.4 Variables

Variables will be assessed using a combination of CPT® codes, Hierarchical Ingredient Code List (HICL) codes, NDCs, ICD-10-CM codes, and HCPCS codes. HICL is a proprietary hierarchical coding system that groups therapies based on generic name. A combination of HCPCS, HICL, and NDCs will be used to identify medications assessed in this study.

7.4.1 Exposures

7.4.1.1 Nemolizumab

Use of nemolizumab will be identified by the presence of the following NDC on the pharmacy claims:

- NDC 0299622015 Nemludio 30 mg pen injector

This list will be updated annually, and additional NDCs will be included as they become available.

7.4.1.2 Comparator AD and PN Treatments

Use of other AD and PN treatments will be identified using NDCs on pharmacy claims and drug administration codes on medical claims.

- Dupilumab
 - NDC 00024591100 Dupixent syringe 100mg/0.67 syringe
 - NDC 00024591102 Dupixent syringe 100mg/0.67 syringe
 - NDC 00024591400 Dupixent syringe 300 mg/2ml syringe
 - NDC 00024591401 Dupixent 300 mg/2ml syringe
 - NDC 00024591500 Dupixent pen 300 mg/2ml pen injector
 - NDC 00024591501 Dupixent pen 300 mg/2ml pen injector
 - NDC 00024591502 Dupixent pen 300 mg/2ml pen injector
 - NDC 00024591520 Dupixent pen 300 mg/2ml pen injector
 - NDC 00024591800 Dupixent syringe 200mg/1.14 syringe
 - NDC 00024591801 Dupixent 200mg/1.14 syringe
 - NDC 00024591802 Dupixent 200mg/1.14 syringe
 - NDC 00024591900 Dupixent pen 200mg /1.14 pen injector
 - NDC 00024591901 Dupixent pen 200mg /1.14 pen injector
 - NDC 00024591902 Dupixent pen 200mg /1.14 pen injector
 - NDC 00024591920 Dupixent pen 200mg /1.14 pen injector
- Lebrikizumab
 - NDC 00002777201 Ebglyss pen 250 mg /2ml pen injector
 - NDC 00002777211 Ebglyss pen 250 mg /2ml pen injector
 - NDC 00002779701 Ebglyss syringe 250 mg /2ml syringe
 - NDC 00002779711 Ebglyss syringe 250 mg /2ml syringe
- Tralokinumab

- NDC 50222034602 Adbry 150 mg /ml syringe
- NDC 50222034604 Adbry 150 mg /ml syringe
- NDC 50222034622 Adbry 150 mg /ml syringe
- NDC 50222034692 Adbry 150 mg /ml syringe
- NDC 50222035000 Adbry autoinjector 300 mg /2ml auto injector
- NDC 50222035001 Adbry autoinjector 300 mg /2ml auto injector
- NDC 50222035002 Adbry autoinjector 300 mg /2ml auto injector

The list of comparator treatments will be reviewed and updated prior to the final report.

7.4.2 Outcomes

During eligible follow-up, occurrence of pregnancy and infant outcomes will be identified through the presence of corresponding codes in the database. Published, validated algorithms will be used when available. The pregnancy outcomes will include ectopic pregnancy, elective termination, live birth, preterm birth, spontaneous abortion, and stillbirth, while infant outcomes are MCMs (primary outcome) and SGA birth. Code lists for all outcomes can be found in [Appendix E](#).

7.4.2.1 Pregnancy Outcomes

7.4.2.1.1 Ectopic Pregnancy

Ectopic pregnancy is defined as the implantation of a fertilized egg in an anatomic location other than the uterus. It will be identified on the maternal record based on ICD-10-CM diagnosis and procedure codes found in [Appendix E](#).

7.4.2.1.2 Elective Termination

Elective termination is defined as an intervention to end a pregnancy prior to delivery. It will be identified on the maternal record based on diagnosis and procedure codes found in [Appendix E](#).

7.4.2.1.3 Live Birth

Live birth is defined as a delivered fetus with any sign of life (e.g., voluntary movement, heartbeat) regardless of gestational weeks. Live births will be identified on maternal records using ICD-10-CM diagnosis and procedure codes found in [Appendix E](#).

7.4.2.1.4 Preterm Birth

Preterm birth is defined as a live birth occurring before the 37th week of pregnancy based on LMP. It will be identified on maternal records based on ICD-10-CM O60.1* diagnosis codes and on infant records based on ICD-10-CM P07.2* and P07.3* codes, as described in [Appendix E](#). Based on a validation study, a similar algorithm had a PPV of 92.3% (95% CI 82.1, 100.0; [Chomistek et al., 2023b](#)).

7.4.2.1.5 Spontaneous Abortion

Spontaneous abortion or miscarriage is defined as pregnancy loss prior to 20 weeks of gestation. Ectopic and molar pregnancies will not be considered spontaneous abortions. Spontaneous abortion will be defined on maternal records as at least 1 ICD-10-CM diagnosis and/or procedure code found in [Appendix E](#). In a validation study, this algorithm had a PPV of 84.7% (95% CI 78.3, 91.2; [Chomistek et al., 2023b](#))

7.4.2.1.6 Stillbirth

Stillbirth will be defined as foetal loss at or after 20 weeks of pregnancy. It will be identified on the maternal record using the following algorithm:

- Presence of an ICD-10-CM code for stillbirth or intrauterine foetal death and an ICD-10-CM code indicating a gestational age greater than or equal to 20 weeks recorded within the period 28 days before (and including) the date of the stillbirth or intrauterine foetal death
PLUS
- At least two ICD-10-CM codes for stillbirth, intrauterine foetal death, or continuing pregnancy after intrauterine foetal death (unspecified trimester, second trimester, or third trimester) identified on or within 7 days
OR
- No other pregnancy outcome ICD-10-CM code (e.g., for live births, spontaneous abortions, elective terminations) identified on the date of the stillbirth or intrauterine foetal death.

The list of ICD-10-CM diagnosis codes can be found in [Appendix E](#). In a validation study, this algorithm had a PPV of 82.5% (95% CI 70.9, 91.0; [Andrade et al., 2021](#)).

7.4.2.2 Infant Outcomes

7.4.2.2.1 MCM

MCMs will be defined based on guidelines from the New York State Department of Health Congenital Malformations Registry, National Birth Defects Prevention Network, and/or the European Surveillance of Congenital Malformations. Live births will be followed for up to one year to identify MCMs that may not be detected until after birth. All identified MCMs will be counted, overall, and classified by body system. Operational definitions may be modified to add or remove MCM-specific ICD-10-CM codes based on clinician input or newly identified algorithms in the literature. Minor congenital malformations will not be included in this definition. A list of ICD-10-CM diagnosis codes for MCMs can be found in [Appendix E](#).

7.4.2.2.2 SGA Birth

An SGA birth is defined as an infant with birthweight below the 10th percentile for their gestational age at birth. It will be identified on infant records based on the ICD-10-CM diagnosis codes found in [Appendix E](#).

7.4.3 Covariates

Members of the study cohorts will be described according to baseline covariates, including demographics, healthcare utilization, comorbidities, pregnancy history and risk factors for the study outcomes, and AD and PN history and treatments. In the claims databases, characteristics will be assessed in the pharmacy and medical claims, while in Optum's Market Clarity Data patient characteristics will be assessed using the patient, procedure, and diagnosis tables from the EHR as well as the pharmacy and/or medical claims. Unless otherwise specified, diagnoses will be identified through the presence of ICD-10-CM codes, while prescription medications will be identified by NDCs through pharmacy dispensings. No over-the-counter medications will be assessed. Drug use and disease status will be categorized as yes (code present) or no (no code present). In addition to the covariates listed below, the 50 most common diagnoses, procedures, and medications will be described during the baseline period. Code lists for the covariates will be provided in the SAP.

